8.2.2. Safety Analyses

Safety data will be presented in tabular and/or graphical format and summarized descriptively, where appropriate. Safety data will be summarized according to Pfizer standards.

Adverse events will be reported according to the 3-tier approach.

Two sets of 'All Causality' and 'Treatment Emergent' adverse events will be summarised. The first set will contain adverse event data for patients while they were taking Tofacitinib. This AE table will summarise AEs under one treatment heading for Tofacitinib (which includes monotherapy and combination therapy). A drug lag of 28 days will be used to assign treatment emergence to Tofacitinib. The AE listings will also list the individual drugs that were being taken at the time of the AE. The second set will include a separate listing of AEs which occurred under another DMARD, following cessation of Tofacitinib. For the cases where the patient continues to be observed for the full duration of the study following discontinuation of Tofacitinib.

NOTE: A lag of 28 days will be applied following cessation of Tofacitinib in the first table. The non-Tofacitinib listing will apply a drug lag of 0 days. Therefore an event which starts on the first day of a new treatment, e.g. Enbrel will be assigned to Tofacitinib in the first table if the AE is within 28 days of Tofacitinib, and also in the listing as the AE started after the initiation of Enbrel. Therefore any event which occurs during a 28 day lag of discontinuing Tofacitinib will appear under Tofacitinib in the first table, and under the new treatment in the listing.

The treatment patterns of RA patients (as defined in [Section 6.2](#)) and the duration of Tofacitinib treatment will be summarized to include n and the percentage in each treatment pattern category. The time to first treatment change (as defined in [Section 6.2](#)) will also be summarized overall and by treatment pattern.

Safety analyses will use the Safety Analysis Set.

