9.4.2.4. Patient Withdrawal

Subjects experiencing AEs as listed in the Xeljanz SmPC [with particular attention paid to Sections 4 (Contraindications), 5 (Special Warnings and 6 (Precautions)] should be monitored and if indicated, treatment should be withdrawn according to provision of the respective SmPC. If treatment with Tofacitinib or other DMARDs is withdrawn patients are followed up until the end of the observation period unless they withdraw from the study (see [Section 9.3](#)).

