9.4.30. Safety Criteria

In contrast to the usual procedure for clinical trials in observational trials the treatment decision is independent of the protocol. Additionally selection criteria of patients at baseline are not as strict as for clinical trials. Thus, this study can provide new insights into the safety of Tofacitinib in routine care. All adverse events (AEs) that will occur during the observation period will be documented. Additionally, at the end of the observation both, the physician and the patient will be asked the general tolerability of the treatment with tofacitinib and reasons for premature discontinuation rates will be analysed.

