6.2. Safety Endpoints

The reporting of safety data will be in accordance with Pfizer Data Standards.

Safety endpoints in this study include the incidence of all adverse events (AEs) and serious adverse events (SAEs). These will be summarized by the treatment group 'Tofacitinib' (see [Section 8.2.2](#)).

The treatment patterns of RA patients prescribed Tofacitinib in a real-world setting will also be described. Patients will be classified into 6 discrete categories as follows:

1. Tofa Mono

Patients who receive Tofacitinib as a monotherapy throughout the study.

2. Tofa Combo

Patients who receive Tofacitinib in combination with another DMARD throughout the study.

3. Tofa Mono to Combo

Patients who start the study receiving Tofacitinib as a monotherapy and then switch to Tofacitinib in combination with another DMARD.

4. Tofa Combo to Mono

Patients who start the study receiving Tofacitinib in combination with another DMARD and then switch to Tofacitinib as a monotherapy.

5. Tofa Mono to Other Treatment

Patients who start the study receiving Tofacitinib as a monotherapy and then discontinue Tofacitinib and switch to another DMARD.

6. Tofa Combo to Other Treatment

Patients who start the study receiving Tofacitinib in combination with another DMARD and then discontinue Tofacitinib.

The duration of treatment with Tofacitinib (in days) will be calculated as:

Date of permanent Tofacitinib discontinuation – Start Date of Tofacitinib treatment + 1

In addition, the time to first treatment change will be calculated:

Date of treatment change – Study Start Date + 1

Where a treatment change is defined as the start of a new treatment or the discontinuation of a current treatment.

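### Adverse events starting more than 28 days after tofacitinib stops, in patients on no DMARD, fall in neither of the two displays planned in SAP 8.2.2

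*SAP*

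**What the plan says.** SAP 8.2.2 describes two adverse-event sets and no others.

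- **First set.** "The first set will contain adverse event data for patients while they were taking Tofacitinib", with monotherapy and combination under one heading. "A lag of 28 days will be applied following cessation of Tofacitinib in the first table".
- **Second set.** "The second set will include a separate listing of AEs which occurred under another DMARD, following cessation of Tofacitinib". "The non-Tofacitinib listing will apply a drug lag of 0 days". An incomplete sentence follows the definition: "For the cases where the patient continues to be observed for the full duration of the study following discontinuation of Tofacitinib".

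The section explains that one event can appear in both sets. It does not mention events that appear in neither.

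On follow-up, Protocol 9.4.2.4 states: "If treatment with Tofacitinib or other DMARDs is withdrawn patients are followed up until the end of the observation period". The only exception it makes is for those who leave the study. Protocol 9.2 and SAP 2.2 likewise continue follow-up through treatment changes. On collection, Protocol 9.4.30 states: "All adverse events (AEs) that will occur during the observation period will be documented". SAP 6.2 names the incidence of AEs and SAEs as the safety endpoints, and adds that they are summarised by the treatment group tofacitinib, with a reference to Section 8.2.2.

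**The concern.** The second set is defined by receipt of another DMARD, not by time since tofacitinib was stopped. A patient can stop tofacitinib, start nothing else and stay in the study, and the protocol foresees exactly that continued observation. Once 28 days have passed, that patient's new adverse events are collected but have no place in either planned display.

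Protocol 9.4.2.4 anticipates withdrawal of treatment because of adverse events, so patients who stopped for safety reasons could plausibly be in this group. Protocol Section 11 lists malignancy and cardiovascular risk among the potential risks, and such events could start later than 28 days after the last dose. What is at stake is whether the study report shows the safety events that were documented in these patients after they stopped.

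**Working it through.** The plan gives no figure to reproduce. The check assigns each kind of follow-up time to the two sets as SAP 8.2.2 defines them.

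| Patient's status when the event starts | First set | Second set |
|---|---|---|
| Taking tofacitinib | yes | no |
| Within 28 days of stopping, on another DMARD | yes | yes |
| Within 28 days of stopping, on no DMARD | yes | no |
| More than 28 days after stopping, on another DMARD | no | yes |
| More than 28 days after stopping, on no DMARD | **no** | **no** |

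The SAP's note on overlap deals with the second row. Nothing deals with the last.

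**How long the uncovered time can be.** Inputs:

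- The lag is 28 days (SAP 8.2.2).
- Observation is 12 months (Protocol 9.4.2), taken to end on Day 365, the Month 12 target day in SAP Appendix A1.1.
- The stop days are assumptions. Days 91 and 183 are the Month 3 and Month 6 target days, and Day 274 is the last day of the Month 6 window, all from the same appendix.
- No DMARD is taken after the stop.

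Formulas: last day in the first set = stop day + 28. Uncovered days = 365 − (stop day + 28).

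| Stop day (assumed) | Last day in first set | Days in neither set | Number of days |
|---|---|---|---|
| 91 | 91 + 28 = 119 | 120 to 365 | 365 − 119 = 246 |
| 183 | 183 + 28 = 211 | 212 to 365 | 365 − 211 = 154 |
| 274 | 274 + 28 = 302 | 303 to 365 | 365 − 302 = 63 |

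These are days for one illustrative patient, not a study total. The documents give no rate of stopping tofacitinib without another DMARD, so no number of affected patients or events can be derived.

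**Whether the same status is missed elsewhere.** In SAP 6.2, the treatment-pattern category for monotherapy patients who leave tofacitinib requires a switch to another DMARD. The treatment subgroups in SAP 5.3 are tofacitinib alone, tofacitinib in combination, and other DMARD. Neither has a place for a monotherapy patient who stops and takes nothing. That fits an oversight better than a deliberate exclusion.

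**The case against.** **The wording may be meant more widely.** The SAP says the second set will include the DMARD listing, not that it consists only of it. It later uses the label non-tofacitinib listing, and the incomplete sentence points to an interest in all observation after discontinuation. The list of tables is a separate document (SAP 9), and SAP 6.2 and 8.2.2 refer to sponsor standards. This shows that wider coverage may have been intended. It does not supply that coverage: the only definition given is receipt of another DMARD, the example in the note uses a new drug, and the incomplete sentence qualifies the definition before it. The content of the list of tables and of the standards is not in the documents.

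**Follow-up may end earlier.** Protocol 9.1 and SAP 2.1 end follow-up at discontinuation, without saying of what. If that meant the drug, the gap would shrink. Protocol 9.2 and 9.4.2.4, SAP 2.2 and SAP 8.2.2 itself all assume that observation goes on after the drug is stopped.

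**Stronger conclusions that a reader might draw.** Four are tempting, and the documents do not support them:

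- *The safety endpoint is not delivered.* SAP 6.2 ties the AE and SAE summary to the treatment group tofacitinib, and the first set supplies that.
- *The reported incidence is biased downward.* The first table describes events on tofacitinib plus 28 days. Leaving out later off-drug events does not bias that quantity.
- *The events go unreported.* Protocol Section 11 has all AEs recorded in the eDCT. All SAEs, and non-serious AEs in the listed risk categories, go to sponsor safety within 24 hours whatever their relatedness.
- *A known share of patients is affected.* The documents give no such figure, and it could be close to zero.

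It is also fair to say that safety is not among the stated objectives (Protocol 8, SAP 2.4), and that listing post-tofacitinib events instead of tabulating them is a presentation choice. Both points limit the importance of the matter. Neither explains why DMARD-free time should be left out of the listing.

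**Conclusion.** The point holds as a gap in the planned end-of-study displays. As SAP 8.2.2 is written, an adverse event that starts more than 28 days after tofacitinib stops, in a patient on no DMARD, is excluded from both sets although the protocol collects it. The rule itself leaves these events out, so this is more than a missing detail.

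The scope is narrow. It covers DMARD-free time only: a combination patient who stops tofacitinib but keeps a csDMARD may count as being under another DMARD. The tofacitinib plus 28-day table is sound for what it describes.

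For an individual patient the uncovered time can be long (63 to 246 days in the illustrations). The effect on the study as a whole is unknown. The conclusion assumes that patients are observed after stopping, as most of the follow-up text says, and that no unseen table list or sponsor standard already adds these events.

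**What to change.** In SAP 8.2.2, redefine the second set as adverse events starting after cessation of tofacitinib, under another DMARD or no DMARD. Show the current treatment and the days since the last tofacitinib dose for each event. Keep the 28-day-lag table unchanged as the tofacitinib-emergent table. Complete or delete the unfinished sentence so that the scope is plain.

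Optionally, add one count of all AEs and SAEs from first dose to end of observation on the Safety Analysis Set, whatever the treatment at the time.

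The cost is SAP wording and a slightly longer listing, plus one table if the optional count is taken up. No new data are needed.

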8.2.3. Efficacy/Effectiveness Analyses

Analyses of the efficacy/effectiveness endpoints will be based on the FAS.

8.2.3.1. Analysis of the Primary Endpoints

The primary endpoints of rate of remission and LDA at month 6 will be analysed as outlined in [Section 8.1.1](#). The rate of remission and LDA will also summarised at each visit as outlined in [Section 8.1.4](#). Missing data will be imputed using the methods outlined in [Section 7](#).

8.2.3.2. Analysis of Secondary Endpoints

The rate of remission and LDA at month 12 will be analysed in a similar manner to the primary endpoint.

The absolute value and change from baseline for DAS28-4 (CRP), DAS28-4 (ESR), HAQ-DI and morning stiffness will be summarised at each visit as outlined in [Section 8.1.2](#).

HAQ-DI categories will be summarised at each visit as outlined in [Section 8.1.3](#).

The change from baseline in EQ-5D, FACIT-Fatigue and WPAI scores will be analysed using MMRM models as described in [Section 8.1.2](#). Absolute values and the change from baseline will also be summarised at each visit as outlined in [Section 8.1.2](#).

Individual domain scores for these three questionnaires will also be summarised at each visit as outlined in [Section 8.1.2](#).

EQ-5D categories will be summarised at each visit as outlined in [Section 8.1.3](#).

The rate of CDAI, SDAI, DAS28-4 (CRP) and DAS28-4 (ESR) remission will be summarised at each visit as outlined in [Section 8.1.4](#). The rate of LDA (assessed by CDAI, SDAI, DAS28-4 (CRP) and DAS28-4 (ESR) respectively) and HAQ-DI response will also be summarised as outlined in [Section 8.1.4](#).

Patient satisfaction with treatment will be summarised as outlined in [Section 8.1.3](#). In addition, patient satisfaction will be summarised by the last treatment received (Tofacitinib or other treatment).

PtGA and PhGA will be summarised at each time-point as outlined in [Section 8.1.2](#).

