8. RESEARCH QUESTION AND OBJECTIVES

The primary objective of this study is to identify clinical and/or biochemical factors that predict achievement of remission or LDA in patients with RA treated with tofacitinib.

The secondary objectives of the study are:

- To describe the treatment patterns of RA patients prescribed tofacitinib in a real-world setting;
- Assess the effect of treatment on patient quality of life and physical function;
- Estimate resource utilization and costs in patients with rheumatoid arthritis (RA) treated with tofacitinib in Greece.

Only a subset of non-serious AEs, collected in the study database, will be reported to Pfizer Safety. This subset will consist of the non-serious AEs that are actively sought due to Pfizer's intention to align with those areas identified as important missing information or a potential risk in the product risk management plan (RMP) of Tofacitinib.

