2.4. Study Objectives

The primary objective of this study is to identify clinical and/or biochemical factors that predict achievement of remission or LDA in patients with RA treated with Tofacitinib.

Logistic regression will be used to investigate the impact of potential predictive factors on remission or LDA at month 6 of treatment.

The secondary objectives of the study are:

- *To describe the treatment patterns of RA patients prescribed Tofacitinib in a realworld setting;*
- *Assess the effect of treatment on patient quality of life and physical function;*
- *Estimate resource utilization and costs in patients with rheumatoid arthritis (RA) treated with Tofacitinib in Greece.*

The secondary objectives will be assessed using descriptive methods unless otherwise stated. Quality of life, measured using the EQ-5D, Functional Assessment of Chronic Illness Therapy (FACIT)-Fatigue Scale and the Work Productivity and Activity Impairment (WPAI) questionnaire, will be analysed using mixed model repeated measures (MMRM) models.

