6.1.2.6. HAQ-DI Response

A HAQ-DI response is defined as a decrease from baseline of at least 0.22 .

The percentage of patients achieving a HAQ-DI response at each time-point (month 3, 6 and 12) will be derived.

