7. HANDLING OF MISSING VALUES

For the primary endpoints of remission and LDA, a non-responder imputation (NRI) will be used for patients who have all components of DAS28-4 (CRP) missing at Month 6. This means that if a patient has all components of the DAS28 (CRP) missing at Month 6, they will be classified as a non-responder (i.e. not having remission or LDA respectively) for the purposes of the primary analyses. If a patient has at least one non-missing component of the DAS28-4 (CRP) at Month 6, then missing components will be imputed by carrying forward the last non-missing post-baseline value, before deriving the DAS28-4 (CRP) at Month 6 in order to determine whether they have achieved remission or LDA at Month 6.

For EQ-5D, FACIT-Fatigue Scale and WPAI, missing data will be handled using

the mixed-effect model as described in [Section 8.1.2](#). In addition, the methods for handling missing data when deriving these scores described below will also be applied.

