7.1. Patient Reported Outcomes (PROs)

For the questionnaires that will be used in the study (EQ-5D, HAQ-DI, FACIT-Fatigue and WPAI), the rules for replacing missing values suggested by the producers of these questionnaires will be followed. If these rules result in the patient having a missing score at a visit, then the missing values will be assumed to be missing at random. Further details of the missing data rules from the relevant scoring guidelines are provided below.

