8.1.2. Analysis of Continuous Data

Unless specified otherwise, continuous variables will be summarised using descriptive statistics (n, mean, standard deviation (SD), median, min, max).

The change from baseline in EQ-5D ([Section 6.1.2.7](#)), FACIT-Fatigue Scale ([Section 6.1.2.8](#)), WPAI ([Section 6.1.2.10](#)) at each time point will be analyzed using mixed models for repeated measures (MMRM), with time-point as a fixed effect; the baseline value will be entered in the model as a covariate, alongside the baseline by time-point interaction. Any missing observations will be set to missing and the MMRM model will assume data are missing at random. Subjects will be fitted as a random effect where an unstructured covariance structure will be used to model the within-subject errors. The Kenward-Roger

approximation will be used to estimate denominator degrees of freedom. If the model fails to converge autoregressive 1 will be fitted instead.

The SAS procedure PROC MIXED will be used to perform the MMRM analysis.

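### HAQ-DI change is summarised on observed cases only, with no model or interval, although the SAP assumes missing HAQ-DI scores are missing at random and fits an MMRM to the other three questionnaires

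*SAP*

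**What the plan says.** Protocol 8 sets one secondary objective with two halves: "Assess the effect of treatment on patient quality of life and physical function". SAP 2.4 sets the default, "The secondary objectives will be assessed using descriptive methods unless otherwise stated", and then makes an exception for EQ-5D, FACIT-Fatigue and WPAI.

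For those three instruments:
- SAP 8.2.3.2: "The change from baseline in EQ-5D, FACIT-Fatigue and WPAI scores will be analysed using MMRM models". Their values and changes are also summarised descriptively by visit.
- SAP 7: "For EQ-5D, FACIT-Fatigue Scale and WPAI, missing data will be handled using" the mixed-effect model.

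For HAQ-DI:
- SAP 8.2.3.2: "The absolute value and change from baseline for DAS28-4 (CRP), DAS28-4 (ESR), HAQ-DI and morning stiffness will be summarised at each visit". The method is that of SAP 8.1.2: "continuous variables will be summarised using descriptive statistics (n, mean, standard deviation (SD), median, min, max". No confidence interval is listed.
- Two further summaries are planned, HAQ-DI categories by visit and a response rate. SAP 6.1.2.6: "A HAQ-DI response is defined as a decrease from baseline of at least 0.22". Under SAP 8.1.3 and 8.1.4 the percentages use only patients with data at that visit.
- HAQ-DI does not appear in the summary table in SAP 8.2.5.
- SAP 7.1.1 covers missing domains within a completed form. Nothing covers a missed visit.

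SAP 7.1 names all four questionnaires. Where the scoring rules still leave no score at a visit, "then the missing values will be assumed to be missing at random".

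**The concern.** The SAP states one missing-data assumption for four questionnaires and plans an analysis that is valid under it for three. If missingness depends on a patient's earlier response, the likelihood model uses the earlier visits and the observed-case mean does not. Should patients with less improvement attend less often, the Month 6 and Month 12 HAQ-DI means, categories and response rate would describe a favourable subset.

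A second gap does not depend on missing data. The objective is to assess an effect on physical function, yet the plan gives no model estimate and no interval for the instrument that measures it.

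**Working it through.** **Plan's own figure.** The documents give no figure on this point. The only calculated quantity is the study size in Protocol 9.5, N = 10k/p = 10 × 10 / 0.50 = 200. It reproduces, and it carries no allowance for missing data.

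**Inputs.** The documents supply the 0.22 threshold (SAP 6.1.2.6) and the missing-at-random assumption (SAP 7.1). All other inputs are assumptions:
- Month 12 mean change −0.40;
- SD of change (s) 0.5 to 0.6;
- correlation of Month 3 with Month 12 change (ρ) 0.5 to 0.7;
- dropout after Month 3 (d) 5% to 30%;
- odds ratio of dropout per SD worse Month 3 change (OR) 1.00, 1.65 or 2.72.

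**Observed-case mean.** Let Z be the standardised Month 3 change, with higher values worse. Dropout follows logit P = a + ln(OR) × Z, with a chosen so that the overall rate is d. Then

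bias of the observed-case Month 12 mean = ρ × s × E[Z | retained].

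E[Z | retained] comes from integrating over the normal distribution. The smallest bias uses ρ × s = 0.5 × 0.5 = 0.25, and the largest uses 0.7 × 0.6 = 0.42. A negative bias means that improvement is overstated.

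| d | OR | E[Z given retained] | × 0.25 | × 0.42 |
|---|---|---|---|---|
| any | 1.00 | 0 | 0 | 0 |
| 5% | 1.65 | −0.0247 | −0.006 | −0.010 |
| 5% | 2.72 | −0.0471 | −0.012 | −0.020 |
| 10% | 1.65 | −0.0488 | −0.012 | −0.020 |
| 10% | 2.72 | −0.0908 | −0.023 | −0.038 |
| 20% | 1.65 | −0.0962 | −0.024 | −0.040 |
| 20% | 2.72 | −0.1732 | −0.043 | −0.073 |
| 30% | 1.65 | −0.1427 | −0.036 | −0.060 |
| 30% | 2.72 | −0.2528 | −0.063 | −0.106 |

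Against the 0.22 threshold, the range at 5% dropout is 0.006/0.22 = 3% to 0.020/0.22 = 9%. At 20% dropout it is 0.024/0.22 = 11% to 0.073/0.22 = 33%.

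**Likelihood estimate.** With monotone dropout, the estimate adds slope × (Month 3 mean of all − Month 3 mean of those retained) to the observed-case mean. That term equals −ρ × s × E[Z | retained], so it cancels the bias exactly. This two-visit calculation is a simplified stand-in for the SAP's MMRM, without the baseline terms or the Month 6 visit.

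**Response rate.** The true rate is Φ((0.40 − 0.22)/s), which is 64.1% for s = 0.5 and 61.8% for s = 0.6. The observed-case rate is too high by 0.5 to 1.3 percentage points at 5% dropout and by about 2 to 5 points at 20%.

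**If dropout depends on the unobserved Month 12 value.** At 20% dropout the observed-case mean is biased by 0.048 to 0.104 units and the likelihood estimate by 0.025 to 0.080. The model reduces this bias but does not remove it.

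**The case against.** The strongest reply is that this is a declared choice. Protocol 9.7.3.2.1 and 9.7.3.4 make the same split, SAP 2.4 makes description the default, SAP 4 has no formal hypotheses, and Protocol 9.9 discloses the bias risk of as-observed analyses. That stands: the SAP follows the protocol here. It does not explain why one half of a joint objective is modelled and the other is not, and it does not reconcile SAP 7.1 with an observed-case mean.

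Two stronger readings are tempting, and the documents do not support them.

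- *Improvement will be overstated because poor responders leave.* Nothing says that they leave. Protocol 9.5 expects minimal missing data. Protocol 9.2 and 9.4.2.4 continue follow-up after a treatment change or withdrawal, and Protocol 9.4.1 keeps patients who miss visits. On the other side, Protocol 9.1 ends follow-up at discontinuation, without saying of what. Protocol 9.4.3 makes no visit mandatory, and Protocol 9.9 anticipates uncompleted questionnaires. The direction is conditional and the amount is open.
- *HAQ-DI results cannot be compared with those of the other questionnaires.* SAP 8.2.3.2 gives the other three the same descriptive summaries, so a like-for-like comparison is available.

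Two smaller points also stand. An observed-case interval can be worked out from n, mean and SD. EQ-5D covers mobility, self-care and usual activities, so function is not wholly unmodelled.

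**Conclusion.** The point holds as a mismatch between the SAP's stated assumption and its planned HAQ-DI analysis, together with a missing interval estimate. It is not evidence that the HAQ-DI result will be wrong.

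At the low missingness that the protocol expects, taken here as 5%, the possible overstatement is at most 0.020 units in these scenarios. At 20% response-related dropout it reaches 0.024 to 0.073 units. It is zero at any dropout rate if dropout is unrelated to response. These sizes rest on the assumed SD, correlation and dropout strength. The assumed mean change affects only the response-rate figures. The mismatch and the missing interval need no such assumptions.

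This is a worthwhile improvement to a secondary analysis. It does not touch the primary endpoint.

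**What to change.** - Add HAQ-DI change to the MMRM in SAP 8.1.2, 8.2.3.2 and the table in 8.2.5, with the terms already specified (time point, baseline, baseline by time point).
- Report the LS mean change with 95% CI and the number observed at Months 3, 6 and 12. Keep the descriptive summaries, the categories and the response rate.
- Adding DAS28 change to the model is optional. DAS28-4 (CRP) already supports the modelled Month 6 and Month 12 endpoints, with non-responder imputation.
- Say in the SAP that the model rests on missing at random and omits patients with no post-baseline data, who are outside the Full Analysis Set. A sensitivity analysis for data not missing at random, and a response rate that counts missing as non-response, would show how much this matters.
- Reconcile Protocol 9.1 with Protocol 9.2 and 9.4.2.4 (repeated in SAP 2.1 and 2.2) on follow-up after discontinuation, because this largely determines how much HAQ-DI data will be missing.
- Settle SAP 7.1.1, which both sets the score to missing and averages the remaining domains when two domains are missing.

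The cost is a few lines of SAP text and one more run of a model already planned for three instruments, with no new data. Protocol 9.7 lets the SAP modify the plan and reserves a protocol amendment for major changes to the primary endpoint definitions or their analyses. The statement in SAP 1 that nothing differs from the protocol would need updating.
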